1.2 Study Flow Diagram

[figure not shown]

[°] The patient's care provider has determined the patient needs an EGD for variceal screening or surveillance. The decision to perform this EGD is not protocol-driven; it is the independent decision of the patient's care provider.

^b The **intended population** for the HepQuant SHUNT Liver Diagnostic Kit (test) is persons with chronic liver disease (CLD) with cirrhosis (Child-Pugh (CP) A or B but without a history of variceal hemorrhage, refractory ascites, or refractory encephalopathy), suspected cirrhosis (positive surrogate tests for cirrhosis), or, advanced fibrosis with low platelet count, who are selected for future esophagogastroduodenoscopy (EGD) to screen for varices. The **intended use** is to provide the clinician with the likelihood of finding large esophageal varices if the EGD is performed. This information may aid the clinician in the decision to proceed with or avoid the EGD. Cirrhosis may be diagnosed histologically, biochemically, clinically, radiologically, or by liver stiffness measurements.

^c Subjects with F3 stage of fibrosis on liver biopsy, or F3 by a surrogate test, who also have a low platelet count, <175,000 μ L⁻¹, may have undetected cirrhosis, portal hypertension, and varices.

1.3 Visit Schedule and Procedures

1.4 Schedule of Activities (SoA)

Visit 0, Screening (Up to 28 days prior to enrollment)

The subject will meet with the study coordinator to obtain informed consent, review study protocol and procedures, address questions or concerns, and determine eligibility. The study coordinator will ensure that subject satisfies all inclusion criteria and does not meet any of the exclusion criteria, that the subject satisfies CLD criteria and etiology, and that the EGD procedure is scheduled or in the process of being scheduled.

The following tests will be obtained at the screening visit: complete blood count, blood chemistry profile, urine pregnancy test for women of child-bearing potential, and electrocardiogram. MELD score will be calculated automatically from screening lab results.

The coordinator will also collect reports of the following tests, if performed within a year of enrollment, and the results will be captured in the eCRF:

- Hepatic imaging by either ultrasonography (US), computed tomography (CT), or magnetic resonance imaging (MRI)
 - Record hepatic masses record LiRAD score 1 to 5 if given in report
 - Record patency or occlusion of main portal vein
- Liver biopsy
 - Scoring system (METAVIR, ISHAK, NASH-CRN, other)
 - Fibrosis stage
 - Necro-inflammatory grade
 - Steatosis grade
- Elastography
 - Type of technology used for elastography measurement
 - kPa and associated stage of fibrosis
 - CAP, or similar score, and grade of steatosis
- Blood Panel or Blood Biomarkers
 - Type of test (ELF, other)
 - Fibrosis stage
 - Necro-inflammatory grade
 - Steatosis grade
- HVPG
 - Free hepatic vein pressure (FHVP)
 - Wedged hepatic vein pressure (WHVP)
 - HVPG matches WHVP FHVP

The above tests are not a requirement for enrollment and are not analyzed for EGD endpoints. The results are collected only to further characterize the CLD study population.

Visit 1, Enrollment (Day 1)

The study coordinator will verify the eligibility of the study subject by review of results from the screening visit. *Note that the Screening and Enrollment visits can be conducted on the same day if results from screening labs are available.* Concomitant medications, demographic information, including gender, race/ethnicity, age (date of birth), height, and weight will be recorded. BMI will be calculated from height and weight. The PI will complete a medical history and physical examination. Child-Pugh (CP) score will be calculated from the screening laboratory tests and the results of the history and physical examination. The coordinator will schedule the subject for the HepQuant SHUNT Test which must be completed within 28 days of Visit 1.

Visit 2, HepQuant SHUNT Test Administration (Up to 28 days after Enrollment Visit)

Visit 1 (Enrollment) and Visit 2 (SHUNT Test) may occur on the same day. The HepQuant SHUNT test must be completed within 28 days of Visit 1 and **prior to the performance of the EGD**. Prior to Test administration the coordinator will record Vital Signs. The HepQuant SHUNT Test will be administered according to the Instructions for Use and the required information will be recorded in the Test Requisition Form (TRF). The coordinator will oversee and confirm all procedures related to receipt, administration, and sample handling for the HepQuant SHUNT test, ensure completion of the "Self-Reported Subject Tolerability" survey, and record any and all AEs and SAEs.

Visit 3, Post-Test Follow-Up (Between 2 and 30 days after SHUNT administration at Visit 2)

The post-Test follow-up visit must be done at least 2 days after the HepQuant SHUNT Test administration, but must be completed within 30 days of SHUNT Test administration. The PI will perform an interim history and physical exam with a focus on any expected and unexpected AEs and SAEs. Vital signs will be obtained. Fasting blood will be obtained for complete blood count, and serum chemistry. This visit can occur at the time of EGD, if EGD falls within the 2-30 day window between Visit 2 and Visit 3.

Collection of EGD Data (EGD must occur within 42 days of SHUNT test at Visit 2)

The EGD must be performed **after** the HepQuant SHUNT Test and within (not more than) 42 days after the HepQuant SHUNT test.

The time interval of 6 weeks, or 42 days, between the HepQuant SHUNT test and EGD allows for logistical complexities in scheduling or rescheduling. Also, the time interval of 6 weeks is short, relative to the generally slow progression from no varices to varices or from small to large varices. From the known rates of progression, varices are unlikely to either develop or change in size within the 6 weeks between SHUNT test and EGD. Section 2.2.2, page 16, defines and discusses the rates of development or progression of varices in reference to the time interval of up to 6 weeks between SHUNT test and EGD. Given the study design with 0 to 42 days between SHUNT test and EGD, it is highly likely that the average time interval between SHUNT test and EGD will be far less than 6 weeks.

If convenient for the patient, the EGD can be done on the same day as the HepQuant SHUNT test (Visit 2); but, if this occurs, the EGD must be done after the HepQuant SHUNT test. The study coordinator will obtain de-identified EGD report and photos and record the EGD results, and upload the EGD report and associated photos into the EDC system. We will also record the plan of treatment in response to the EGD findings. EGD findings are NOT recorded as adverse events.

All required eCRFs will be completed at each of the study visits.

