Abbreviations: Retro, retrospective study; Pro, prospective study; N, number of subjects; EtOH, alcohol-related liver disease; Viral, chronic viral hepatitis due to either HBV or HCV; NAFLD, non-alcoholic fatty liver disease; CP A, Child Pugh class A cirrhosis; LSM, liver stiffness measurement; EGD, esophagogastroduodenoscopy (endoscopy); t, LSM-EGD, time interval between performance of the LSM and performance of the EGD; Pltl, platelet count in μ L⁻¹. ¹From Marot, et al (6). All studies used LSM and platelet count with cutoffs similar to BAVENO VI criteria. The sample size of the HALT-C Training dataset was similar to the sample sizes of the individual studies and also similar in terms of etiology of CLD, male dominance, mean age, Child-Pugh class, and time interval between performance of the test and EGD. ²Large esophageal varices are varices of diameter 5 cm or more, or described as medium or large, or graded as 2 or higher. Large esophageal varices are considered high risk for variceal hemorrhage and its consequent morbidity and mortality. Large esophageal varices are varices that need treatment.

Published studies evaluating the BAVENO VI Criteria. Ten published studies, encompassing 2977 cases, using LSM and platelet count and criteria similar to BAVENO VI have focused on the need to identify the CLD patient at low likelihood of having large esophageal varices (3-11,28-30,38) (Table 1). In these reports, viral hepatitis was the most common etiology, followed by alcohol and NAFLD/NASH. Most were men with a mean age in the mid-50s. All had a diagnosis of cirrhosis and nearly all had Child-Pugh class A disease severity. These reports do not include subjects with either noncirrhotic fibrosis or Child-Pugh class B cirrhosis. The cases from the published literature have selected characteristics that are similar to the subjects in the HALT-C Training Dataset (Table 1).

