Avoiding unnecessary EGD is a goal of screening. The percentage of unnecessary EGDs is defined by the number of cases with no or small varices that underwent EGD that would have avoided EGD by application of selection criteria. A meta-analysis of the 10 published studies suggested that application of BAVENO VI criteria might reduce screening or surveillance EGDs by 7% to 30% (6). Each of the 10 studies applied different combinations of cutoffs for platelet count (>100,000 μ L-1, >120,000 μ L⁻¹ or >150,000 μ L⁻¹) and LSM (<20 or <25 kPa). The individual study results were pooled, and the pooled estimates were sensitivity 93%, specificity 30%, negative predictive value (NPV) 97%, positive predictive value (PPV) 14%, negative likelihood ratio (NLR) 0.22, positive likelihood ratio (PLR) 1.33 (Table 2), and false negative rate (FNR) 3%. The analysis also revealed that 21 of 319 (6.5%) large varices needing treatment were missed (6). Another review further highlighted the relatively low rate of reduction in EGDs (20% overall) and unacceptably high FNR and rate of missed large varices or varices needing treatment (4).

Study	Prevalence	ТР	FN	FP	TN	Sens	Spec	PPV	NPV	FNR	PLR	NLR
Abraldes	0.15	54	3	238	84	0.95	0.26	0.18	0.97	0.03	1.28	0.20
Ahmed	0.11	49	3	318	108	0.94	0.25	0.13	0.97	0.03	1.26	0.23
Chang	0.08	11	3	128	31	0.79	0.19	0.08	0.91	0.09	0.98	1.10
Ding	0.10	26	0	138	107	1.00	0.44	0.16	1.00	0.00	1.78	0.00
Maurice	0.05	13	2	195	100	0.87	0.34	0.06	0.98	0.02	1.31	0.39
Paternostro	0.21	19	0	61	10	1.00	0.14	0.24	1.00	0.00	1.16	0.00
Puigvehi	0.15	45	10	174	139	0.82	0.44	0.21	0.93	0.07	1.47	0.41
Silva	0.18	20	0	80	12	1.00	0.13	0.20	1.00	0.00	1.15	0.00
Thabut	0.08	49	0	445	156	1.00	0.26	0.10	1.00	0.00	1.35	0.00
Tosetti	0.08	12	0	95	39	1.00	0.29	0.11	1.00	0.00	1.41	0.00
Pooled Totals	0.11	298	21	1872	786	0.93	0.30	0.14	0.97	0.03	1.33	0.22
Means of Studies	0.12	30	2	187	79	0.94	0.28	0.15	0.98	0.02	1.32	0.23
SD of Studies	0.05	17	3	119	52	0.08	0.11	0.06	0.03	0.03	0.21	0.35
HALT-C	0.10	21	1	89	106	0.95	0.54	0.19	0.99	0.01	2.09	0.08

Table 2: Diagnostic Performance of LSM + Platelet Count versus DSI for Likelihood of Large Esophageal Varices

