3 OBJECTIVES AND ENDPOINTS

OBJECTIVES	ENDPOINTS	JUSTIFICATION FOR ENDPOINTS
Primary		
The primary objective of this study is to validate DSI ≤18.3 for identifying subjects with CLD selected for future EGD for variceal screening or surveillance who are not likely to have large esophageal varices ("Rule Out").	The endpoint for the primary objective is the negative likelihood ratio (NLR) for large esophageal varices. The performance goal for validation of DSI ≤18.3 is the upper limit of the confidence interval (CI) for NLR to rule out NLR > 0.52, in addition the observed sensitivity must be > 0.85. The confidence level for the confidence interval will be adjusted in order to maintain a one-sided type I error rate of 0.025 as described in section 9.5.1.	Primary: The current minimally- invasive practice using liver stiffness measurement (LSM) by transient elastography (TE) plus platelet count, yields NLRs from 0 to 1.1. A critical value (cv) of 0.27 for NLR represents the average of results for these studies in ruling out large esophageal varices. The study is designed for superiority over current practice.
Secondary		
The secondary objective is to perform logistic regression analysis of the probability of large esophageal varices for DSI > 18.3. In the HALT-C Training Dataset the probability of large varices increased in proportion to increasing DSI in subjects with DSI above 18.3.	The secondary endpoint is the significance of the logistic regression equation for the relationship of DSI >18.3 to probability of large esophageal varices.	Secondary : Predicted probability of large varices versus DSI will be analyzed by logistic regression analysis and affiliated statistical tests of the significance of the association between the continuous DSI score and risk of large varices. These analytical results will be evaluated using a calibration table in which the prevalence of large varices is tabulated by DSI quartile. A clinician knowing that a high DSI has a high probability of large varices could enhance his sense of urgency to perform EGD.
Tertiary/Exploratory		

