9.1 Statistical Hypotheses

9.1.1 PRIMARY EFFICACY ENDPOINT (DSI ≤18.3 "RULES OUT" LARGE ESOPHAGEAL VARICES).

For each subject, the primary endpoint is the presence of large varices based on EGD examination. The primary estimands are NLR and sensitivity which then define the standard for diagnostic accuracy of DSi as a rule-out test for large varices. A primary objective is to determine whether the NLR for DSI \leq 18.3 is an improvement over the average value for NLR from 10 published studies of 2977 cases of the use of LSM plus platelet count in likelihood of large esophageal varices. Improvement will be decided if the confidence interval for the observed NLR rules out NLR > 0.52, which corresponds to the observed NLR being smaller than the approximate critical value of cv= 0.27. With this partition of the ROC outcome space, the study will conclude that the diagnostic accuracy of DSI < 18.3 is acceptable if the observed NLR is smaller than that observed in most previously published studies (**Figure 10**). The null hypothesis of NLR = 0.52 is chosen to demonstrate improvement over the diagnostic accuracy of tests evaluated in the 10 published studies of 2977 cases.

⁶ A single interim analysis is planned after the trial data set has compete DSI and EGD measurements on a minimum of 250 participants as described in Section 9.5.1.

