9.6.2 EXPLORATORY ANALYSES

Exploratory 1 (AUROC of DSI for large esophageal varices): The c-statistic for the AUROC for DSI in likelihood of large esophageal varices will be compared to the c-statistic for the AUROC of LSM plus platelet count in likelihood of large esophageal varices. The most complete study with publication of AUROCs for LSM plus platelet count is from Abraldes, et al (8) where the AUROC was 0.76 for varices needing treatment (large varices or small varices with red signs). Given this benchmark the performance goal is an AUROC \geq 0.76 for DSI in likelihood of large esophageal varices.

In addition, we will examine the diagnostic performance (sensitivity, specificity, PPV, NPV, NLR, PLR, FNR, miss rate⁸) of DSI over the full range of DSI to define the Optimal DSI for "Rule Out" – highest sensitivity and NPV with lowest FNR. We will also compare the diagnostic performance of this "optimum" DSI to DSI 18.3. The purpose of this analysis is to provide upside and downside performance of DSI around the validated cutoff of DSI 18.3.

This analysis will yield a table of sensitivities, specificities, NPVs, PPVs, NLRs, PLRs, FNRs, and miss rates⁸ over the given range of DSI that could be included in a package insert to help the clinician interpret a given DSI result.

AUROCs of DSI in likelihood of large varices will be constructed for individual etiologies of disease with over 100 subjects and for the categories of cholestatic and non-cholestatic liver diseases.

Exploratory 2 (DSI for Small or Any Size of Esophageal Varices). The analyses listed above for primary objective, secondary objective 1, and secondary objective 2 will be repeated using small varices in one set of analyses and any size of varices in another set of analyses.

Exploratory 3 (STAT). The serum concentration of d4-cholate from the 60-minute time point (STAT) of the HepQuant SHUNT test correlates well with DSI (r^2 =0.88). The STAT value represents a simplified, single point version of DSI. For this reason, we propose to evaluate the diagnostic performance of a cutoff for STAT defined from the HALT-C Training dataset for large esophageal varices and esophageal varices of any size.

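### Success is framed as beating liver stiffness plus platelets, but that rule is never evaluated in SHUNT-V patients: its comparator is external and the collected elastography is kept out of the EGD analyses

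*Combined protocol and SAP*

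**What the plan says.** **Objective.** Section 9.1.1 makes it a primary objective to determine whether the NLR at DSI ≤18.3 "is an improvement over the average value for NLR from 10 published studies of 2977 cases of the use of LSM plus platelet count". Section 3 adds: "The study is designed for superiority over current practice". Section 9.5 lists, among the implications of validation, better diagnostic performance and a lower false negative rate than LSM plus platelets.

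**Comparator.** The primary test in Section 9.4.2 is single-arm. The upper confidence limit for NLR must lie below 0.52, and the observed sensitivity must meet a 0.85 criterion. In Section 9.6.2 the AUROC for DSI "will be compared to the c-statistic for the AUROC of LSM plus platelet count", a single published value of 0.76.

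**Populations.** Section 2.2.4 describes the ten published cohorts as all cirrhotic and nearly all Child-Pugh A, and says: "These reports do not include subjects with either noncirrhotic fibrosis or Child-Pugh class B cirrhosis". Section 5 has SHUNT-V enrol non-cirrhotic F3 with low platelets, Child-Pugh A and Child-Pugh B.

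**Data.** For Visit 0, Section 1.4 lists reports to be captured if the test was done within a year of enrolment: imaging, biopsy, elastography (technology and kPa), blood biomarkers and HVPG. It then says: "The above tests are not a requirement for enrollment and are not analyzed for EGD endpoints". The results serve only to describe the population. The blood count, which supplies the platelet count, is listed separately and is obtained from every subject. Sections 4.3.2 and 9.4.3 place platelet count in the multivariable model for large varices.

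**The concern.** A single-arm trial can show that a test meets a fixed goal. It cannot by itself show that the test beats another test, unless the other test's performance carries over to the trial's population. Here the severity and etiology mix differ by the protocol's own account, and sensitivity, specificity and AUROC can all shift with that mix. An observed gap between DSI in SHUNT-V and LSM plus platelets in the published cohorts cannot be assigned to the test.

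One ingredient of a same-patient comparison (platelets) will be available for everyone, and the other (kPa) for an unknown share of subjects. The plan sets the kPa values aside. What is at stake is the comparative claim attached to the result, not the validity of the primary test against 0.52.

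**Working it through.** **1. The plan's own figure.** Inputs (Section 9.2.1): N = 400, 20% prevalence (80 cases, 320 non-cases), sensitivity 0.90, specificity 0.50, NLR 0.20, null 0.52, one-sided 0.025. With Table 9 equation E:

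- Variance of ln NLR = 0.90/(0.10×80) + 0.50/(0.50×320) = 0.1125 + 0.0031 = 0.1156; SE = 0.340.
- Power = Φ(ln(0.52/0.20)/0.340 − 1.96) = Φ(0.85) = 0.80, as in Table 10.
- Critical value = 0.52×exp(−1.96×0.340) = 0.267, as stated (0.27).

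The sample size and power are not in dispute.

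**2. The two populations.**

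| | Published cohorts (Section 2.2.4, Tables 1 and 2) | SHUNT-V (Sections 4.1.1 and 5) |
|---|---|---|
| Severity | 98% Child-Pugh A, weighted by N, in the 9 studies reporting it | F3 with low platelets, Child-Pugh A, Child-Pugh B |
| Viral etiology | 33% to 100% by study | 15% expected |
| Prevalence of large varices | 11% pooled | 20% expected |

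The 98% comes from 2,500 subjects. Seven studies report 100%, one reports 89% of 310 and one 87% of 112, so the share not Child-Pugh A is (34.1 + 14.6)/2,500 = 1.9%. Prevalence alone does not move NLR, as Section 2.2.4 notes; the severity mix can.

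**3. What meeting the primary goal implies.** Take a test with exactly the pooled LSM-plus-platelet performance from the Table 2 counts: sensitivity 298/319 = 0.934, specificity 786/2,658 = 0.296, NLR 0.223. At N = 400 and 20% prevalence:

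- Variance = 0.934/(0.0658×80) + 0.704/(0.296×320) = 0.1774 + 0.0074 = 0.1848; SE = 0.430.
- Probability of passing the NLR criterion = Φ(ln(0.52/0.223)/0.430 − 1.96) = Φ(0.01) = 0.51.
- By simulation with the score test and the sensitivity criterion the probability is 0.60, or about 0.56 with the interim analysis.

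The comparator would itself succeed about as often as not, or somewhat more often. Success therefore does not establish improvement over it.

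**4. What a same-patient comparison could deliver.** The documents do not give the share of subjects with transient elastography; assume 40% to 60%. Take specificity 0.50 for DSI (design value) and 0.30 for LSM plus platelets (pooled, Table 2).

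- At N = 400: 160 to 240 subjects, of whom 32 to 48 are cases and 128 to 192 are non-cases.
- With independent results within patients, the discordant proportions are 0.5×0.7 = 0.35 and 0.5×0.3 = 0.15. The variance of the paired difference is (0.35 + 0.15 − 0.20²)/n = 0.46/n.
- Within-patient dependence is also unknown. The total discordance can range from 0.20 (variance 0.16/n) to 0.80 (variance 0.76/n).

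| Non-cases | 95% half-width, independent | Range over possible dependence |
|---|---|---|
| 128 (N = 400, 40%) | 0.117 | 0.07 to 0.15 |
| 192 (N = 400, 60%) | 0.096 | 0.06 to 0.12 |
| 80 (N = 250, 40%) | 0.149 | 0.09 to 0.19 |
| 120 (N = 250, 60%) | 0.121 | 0.07 to 0.16 |

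A difference of 0.20 would exclude zero in each row. Under independence it needs 0.46×(1.96/0.20)² ≈ 45 non-cases, about 14% of the 320. Stopping at the interim leaves only 20 to 30 cases. That is a likely outcome if the test works: at sensitivity 0.90 and 20% prevalence, Table 13 gives an interim efficacy probability of 0.652 at NLR 0.20 and 0.880 at NLR 0.15.

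**The case against.** The strongest reply is that the external benchmark is declared openly. The core objective is validation of a cutoff in a single-arm study, and the intended use is to aid the EGD decision, not to replace elastography. A performance goal is a legitimate design choice. That stands, and it is why no change to the primary endpoint is asked for. It does not cover the word superiority in Section 3 or the improvement objective in Section 9.1.1.

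Two stronger readings are tempting and are not supported.

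- A reader might infer that platelet results are also barred from analysis against EGD. They are not. The sentence in Section 1.4 follows the list of optional reports, which does not include the blood count, and it cannot mean platelets because a platelet limit is an entry criterion for F3 subjects.
- A reader might infer that every planned comparison is with published data. Sections 4.3.2 and 9.4.3 test DSI against platelets and cirrhosis in the same patients, and STAT is compared with DSI in the same patients. Those models ask whether DSI adds to platelets. They do not evaluate the combined LSM-plus-platelet rule, which needs kPa.

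The reply also says, rightly, that a paired table would be compromised. Elastography is optional, may use different technologies and may be up to a year old, a weakness that Section 2.2.4 criticises in one of the published studies. Everyone enrolled has already been selected for EGD, and F3 subjects must have platelets below 175,000. Both features lower the apparent specificity of LSM plus platelets and so favour DSI. These limits confine the table to an exploratory role.

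**Conclusion.** The point holds in a limited form. The comparative wording in Sections 3, 9.1.1 and 9.5 goes beyond what a single-arm test against NLR 0.52 can show, because the only LSM-plus-platelet figures come from populations that differ in severity and etiology. No section plans to evaluate the combined rule in SHUNT-V subjects, although part of the data will be in the eCRF.

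A paired analysis could estimate the specificity difference to within about 0.10 to 0.12 at N = 400, or 0.12 to 0.15 at N = 250. This assumes 40% to 60% elastography coverage, independence within patients, and a specificity of 0.30 borrowed from the same external cohorts. Sensitivity, on which a rule-out claim turns, would be descriptive only.

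A reader might infer that the paired table would settle whether DSI beats current practice. It would not: the subset is non-random, of unknown size and selected in a direction that favours DSI. Whether 0.52 or 0.27 is the right benchmark is a separate question and is not argued here.

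**What to change.** 1. **Section 1.4, Visit 0:** exempt elastography from the statement that the collected tests are not analysed against EGD.
2. **Section 9.6.2:** pre-specify an exploratory paired comparison in subjects with transient elastography within one year. Compare DSI ≤18.3 with the rule already described in Section 2.2.4 (LSM <20 kPa with platelets >150,000). Use McNemar's test for specificity and for EGDs avoided, describe sensitivity and miss rate, and compare AUROC by DeLong's method against an LSM-plus-platelet score. Report the number of subjects covered and the LSM-to-EGD interval.
3. **Same section:** state that the subset is non-random, and that selection for EGD and the F3 platelet entry rule lower the apparent specificity of LSM plus platelets and so favour DSI. Do not base a superiority claim on this table.
4. **Sections 3, 9.1.1 and 9.5:** describe success as meeting a fixed performance goal (ruling out NLR above 0.52, with the sensitivity criterion), not as superiority over current practice.

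Cost: a minor protocol amendment, which needs IRB approval, and one extra table. There are no new procedures or patients, and the primary endpoint and sample size do not change. The drawback is that the subset may be small, and smaller still if the trial stops at N = 250.
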